9.6. Dose Modification

Dose modification will be summarized by subject group.

The number and percent of subjects who have at least one dose modification, number of dose modification per subject, and type for dose modification including dose increase, reduction, and interruption will be summarized by subject group.

Details of dose adjustments will be provided in a by subject listing.

10. CLINICAL ACTIVITY ANALYSIS

Efficacy endpoints will be analyzed for the Phase 1 and Phase 2 portions of study separately as well as for the combined Phase 1/2 in R/R AML subjects. All efficacy analyses will be performed in the FAS unless otherwise specified. The primary endpoint will be analyzed in the EAS to provide supportive evidence.

Phase 1:

Efficacy analyses will be primarily presented for Phase 1 dose escalation by total daily dose groups, Part 1 Expansion by cohorts, and the combined Phase 1 by malignancy type and by total daily dose of <100 mg, 100 mg, and >100 mg in R/R AML as described in items 1 to 3 of [Section 5.1](#).

Phase 2:

For Phase 2, all efficacy analyses will be conducted for the R/R AML subjects following item 4 of [Section 5.1](#).

Combined Phase 1/2:

Analyses will be conducted primarily for the R/R AML subjects who have received 100mg total daily dose following item 5 of [Section 5.1](#).

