### **12.5. Statistical Methodology**

#### **12.5.1. General Methods**

Tabulations will be produced for disposition, demographic and baseline disease characteristics, safety, PK, PD, and clinical activity parameters and will be presented by dose level, disease and overall. For analyses of safety and unless otherwise specified, subjects treated during the dose escalation phase will be pooled with those receiving the same dose and regimen during the expansion phase. For analyses of clinical activity, summaries will be produced separately for the

dose escalation, by each arm in Part 1 Expansion, and for the Phase 2 portion of the study. Subjects from the dose escalation and Part 1 Expansion, who meet inclusion and exclusion criteria of Phase 2, may be included in efficacy analyses if treated with the same dose and regimen.

Categorical variables will be summarized by frequency distributions (number and percentages of subjects with 95% confidence interval, if applicable) and continuous variables will be summarized by descriptive statistics (mean, standard deviation, median, minimum, and maximum).

All data will be provided in by-subject listings.

The study data will be analyzed and reported based on all subjects' data from the dose escalation and expansion phases up to the time when all subjects have completed at least 6 cycles of treatment regardless of dose interruption or discontinued study drug earlier, or when the follow up is deemed adequate for the assessment of duration of response, whichever is the later date. Any additional data for subjects continuing to receive study treatment or in follow up for HSCT or survival past the data cutoff date for the clinical study report (CSR) will be reported in a final descriptive update at the end of study.

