#### **Statistical Considerations for Phase 2**

Phase 2 is the pivotal part of this study. The primary objective of Phase 2 is to confirm the preliminary clinical activity observed in the dose escalation and Part 1 Expansion in subjects with IDH2 mutated relapsed or refractory AML at the recommended dose/regimen for expansion. The primary analysis of the clinical activity of AG-221 will be based on Investigator's response assessment (CRR, ORR, and duration of remission/response). The FAS will be used. Key supportive analyses will be based on independent central review of response in FAS. Additional analyses of efficacy will be conducted using the EAS/CEAS. Subjects from the

dose escalation and Expansion Part 1 who meet eligibility criteria for the Phase 2 portion of the trial may be included as a supportive analysis of clinical activity if treated with the same dose and regimen.

An observed ORR of at least 33.6% (at least 42 responses in 125 subjects) will result in an exact binomial 95% CI with a lower bound greater than 25%, which is clinically meaningful in this setting and exceeds the ORR expected with available therapies (Roboz, et al. 2014). This will be considered as evidence of clinically significant activity of AG-221.

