4.1.1. Overview of the Phase 1/Dose Escalation Phase

A schematic of the dose escalation scheme is provided in Figure 2. The dose escalation phase will utilize a standard “3+3” design. During the dose escalation phase, consented eligible subjects will be enrolled into sequential cohorts of increasing doses of AG-221. Each dose cohort will plan to enroll a minimum of 3 subjects. The initial dosing regimen was twice daily (BID) (approximately every 12 hours). Based on the emerging data, a once daily (QD) dosing schedule was implemented. Alternative dosing schedules (eg, loading dose followed by QD dosing) may continue to be explored in the dose escalation and expansion phases as agreed upon by the Clinical Study Team. If there are multiple subjects in the screening process at the time the third subject within a cohort begins treatment, up to 2 additional subjects may be enrolled, for a maximum of 5 subjects per cohort, with approval of the Medical Monitor.

Figure 2: Dose Escalation Scheme

* If only 3 subjects were enrolled at the MTD level, an additional 3 subjects will be enrolled to confirm that <2 of 6 subjects experience a DLT at this dose.

Note: CST = Clinical Study Team; DLT = dose-limiting toxicity; MTD = maximum tolerated dose.

The planned study drug doses for the dose escalation phase are summarized in Table 2. The starting dose for this study was 30 mg administered approximately every 12 hours, based on the results of GLP dose range-finding toxicology studies. Based on evaluation of the safety, tolerability, and PK/PD data of the previous dose levels, an intermediate dose level not specified in the tables below may also be explored. The MAD of AG-221 in this portion of the trial is 650 mg administered orally QD.

Confirmation of the primary malignancy is required. Subjects in the dose escalation phase are required to have IDH2 gene-mutated disease, documented by local site testing. Retrospective gene mutation analysis will be conducted at a central laboratory to support contemporaneous companion diagnostic development.

Table 2: Planned Dose Escalation Scheme

BID Schedule AG-221 Dose (mg)	QD Schedule AG-221 Dose (mg)
30 ¹	Not evaluated
50	50
75	75
100	100
150	150
Not evaluated	200
Not evaluated	300
Not evaluated	450
Not evaluated	650

¹ Starting dose.

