5. GENERAL STATISTICAL CONSIDERATIONS

5.1. Reporting Conventions

Tabulations will be produced for subject disposition, demographic and baseline disease characteristics, safety, and clinical activity parameters. The study data will be analyzed and reported for efficacy/safety when applicable based on all subjects' data from the Phase 1 dose escalation, the Part 1 Expansion, the combined Phase 1, Phase 2, and the combined Phase 1/2 up to the data cut-off date of 29 July 2019.

Unless specified otherwise, the data will be presented as specified below:

1. In Phase 1 dose escalation, all subjects (combining different malignancy types [overall]) will be utilized. Data will be summarized by total daily dose groups, unless otherwise specified. The total daily dose is defined as the total dose a subject receives during a day based on the assigned or actual dose regimens for efficacy and safety, respectively.
2. In Part 1 Expansion, all subjects (combining different malignancy types) will be utilized and will be grouped into 4 arms (groups):
 - Arm 1: R/R AML and age ≥ 60 years, or any subject with AML regardless of age who has relapsed following a BMT.
 - Arm 2: R/R AML and age < 60 years, excluding subjects with AML who have relapsed following a BMT.
 - Arm 3: Untreated AML and age ≥ 60 years that decline standard of care chemotherapy.
 - Arm 4: IDH2-mutated advanced hematologic malignancies not eligible for Arms 1 to 3.
3. In the combined Phase 1, analyses will be presented by total daily dose groups as < 100 mg, 100 mg and > 100 mg for subjects with R/R AML. The overall subjects in the combined Phase 1 will be summarized by malignancy type including R/R AML, untreated AML, MDS, and other.
4. In Phase 2, data will be summarized primarily for all R/R AML subjects.
5. In the combined Phase 1/2, R/R AML will be presented by total daily dose groups as < 100 mg, 100 mg and > 100 mg, and the overall subjects will be presented by malignancy type.

For subjects who were discontinued from study treatment, underwent HSCT, and then re-started AG-221, data after restarting AG-221 will be excluded from all summary analyses except for death. The data collected after restarting AG-221 will be provided in listings.

Categorical variables will be summarized by frequency distributions (number and percentages of subjects) and continuous variables will be summarized by descriptive statistics (number of subjects, mean, standard deviation (SD), median, minimum, and maximum).

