10.2. Analysis of Primary Efficacy Endpoint

The primary efficacy endpoint of ORR is defined as the rate of responses including CR, CRi, CRp, PR, mCR (for MDS) and MLFS (for AML) by investigator assessment. The ORR will be summarized by the percentage of responses primarily in the FAS with 2-sided exact binomial 95% CI.

Response will also be summarized by the best objective response following the hierarchical order of CR, CRi/CRp, PR, mCR/MLFS, stable disease, relapse/progressive disease/failure, and not evaluable (NE).

An observed ORR in the pivotal Phase 2 R/R AML FAS subjects with the lower bound of the exact binomial 95% CI greater than 25% is deemed clinically meaningful and exceeds the expected ORR with other available therapies. This will be considered as evidence of clinically significant activity of AG-221. The analyses in the combined Phase 1/2 R/R AML on total daily dose of 100mg utilize larger population and thus provide robust estimate of ORR to better describe the clinical activity of AG-221.

To assess the robustness of the primary analysis, the following sensitivity analyses will be performed:

- (1) ORR in the EAS for the combined Phase 1, Phase 2, and the combined Phase 1/2;

- (2) The ORR assessed by Independent Response Adjudication Committee (IRAC) in the FAS for Phase 1, Phase 2, and the combined Phase 1/2 R/R AML.

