10.4. Subgroup Analysis

Appropriate subgroup analyses for ORR and DOR, CRR, CR/CRh rate, CR/CRi/CRp rate, and OS based on the following variables in the combined Phase 1, Phase 2, and the combined Phase 1/2 R/R AML will be provided using the FAS if data are available and/or clinically meaningful. TTR and TTBR will be summarized by best response by investigator assessment, and transfusion independence rate will be summarized by best response by both investigator and IRAC assessments. The ORR, CRR, CR/CRh rate and CR/CRi/CRp rate by subgroups will be presented in forest plots.

1. Age groups (<60, 60 - <70, 70 - <75, ≥75 years)
2. Gender (male vs female)
3. Region (US vs non-US)
4. Race (white vs non-white)

5. Baseline ECOG PS (Grade 0, 1, 2)
6. Number of prior AML therapies (1, 2, >=3)
7. Prior history of MDS (yes vs no)
8. WHO classification of AML (AML with Recurrent Genetic Abnormalities, AML with Myelodysplasia-Related Changes, Therapy related Myeloid Neoplasms, AML not Otherwise Specified)
9. Prior HSCT for AML (yes vs no)
10. IDH2 gene mutation type (R140 vs R172) for ORR and all secondary endpoints
11. Baseline cytogenetic risk status (poor, intermediate, favorable)
12. Best response by Investigator assessment
13. Best response by IRAC
14. Refractory/Relapse status (primary refractory vs relapse; for combined Phase 1/2 only).
15. R/R AML subtypes (subjects who relapse after allogeneic transplantation; subjects in second or later relapse; subjects who are refractory to initial induction or re-induction treatment; subjects who relapse within 1 year of initial treatment, excluding subjects with favorable-risk status according to National Comprehensive Cancer Network [NCCN] Guidelines [NCCN v1.2015]. Favorable-risk cytogenetics: inv(16), +(16;16), t(8;21), t(15;17); subjects who have failed 2 or more cycles of first line therapy [consisting of an intermediate intensity chemotherapy, hypomethylating agent, or low dose cytarabine]; for combined Phase 1/2 only).

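### The SAP's main combined Phase 1/2 efficacy pool drops the protocol's Phase 2 eligibility and same-regimen conditions, and Section 13 does not list the departure

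*SAP*

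**What the plan says.** Protocol 12.5.1 (General Methods) sets the terms on which Phase 1 subjects may join the Phase 2 efficacy data. They are subjects "who meet inclusion and exclusion criteria of Phase 2, may be included in efficacy analyses if treated with the same dose and regimen". Protocol 12.5.7 (Statistical Considerations for Phase 2) repeats the eligibility condition and says that such subjects "may be included as a supportive analysis of clinical activity if treated with the same dose and regimen".

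SAP Section 10, for the combined Phase 1/2, says: "Analyses will be conducted primarily for the R/R AML subjects who have received 100mg total daily dose". It refers to SAP 5.1 item 5: "In the combined Phase 1/2, R/R AML will be presented by total daily dose groups". SAP 5.1 item 1 gives the meaning of the term: "The total daily dose is defined as the total dose a subject receives during a day based on the assigned or actual dose regimens", with the assigned regimen used for efficacy. SAP 10.2 says that the combined analyses at 100 mg "utilize larger population and thus provide robust estimate of ORR to better describe the clinical activity of AG-221".

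SAP Section 13 lists three changes to the protocol's analyses: the MAA cut-off date, response in place of remission, and added secondary endpoints. The definition of the combined pool is not among them.

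**The concern.** The protocol's pool is one population on one regimen. The SAP's pool is any R/R AML whose assigned doses add up to 100 mg in a day. ORR, CRR, CR/CRh, CR/CRi/CRp, DOR and OS are all planned for the combined group, with subgroup analyses. A reader who knows the protocol would take those estimates to describe Phase 2-type subjects on the Phase 2 regimen. They would in fact describe a wider population and two schedules, and the SAP section meant for such changes would not say so.

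**Working it through.** **1. The plan's own figure.** Protocol 12.1 gives 42/125 = 33.6% with an exact 95% CI of 25.4% to 42.6%. Clopper-Pearson gives 25.40% to 42.60%, and 41/125 has a lower bound of 24.67%, so 42 is the correct minimum. SAP 10.2 applies the 25% criterion to the Phase 2 full analysis set alone. The combined pool does not enter it.

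**2. The two definitions side by side.**

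| Condition | Protocol 12.5.1 and 12.5.7 | SAP 5.1 item 5, 10, 10.2 |
|---|---|---|
| R/R AML | Phase 2 eligibility, so one of four categories (8.2) | any R/R AML |
| Prior IDH inhibitor | excluded (8.3, criterion 22, Phase 2 only) | no condition |
| IDH2 result | central, at screening | no condition; local entry in Phase 1, central testing retrospective |
| Dose | same dose and regimen; Phase 2 starts at 100 mg QD | day's total of 100 mg |
| Status | supportive (12.5.7) | robust estimate (10.2) |

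**3. What the differences let in.**
- *Schedule.* SAP Table 2 lists both 50 mg BID and 100 mg QD. Since 2 × 50 = 100, both fall in the 100 mg group. Dose-escalation efficacy is also tabulated by total daily dose. The tables by assigned dose group use the dose determining set and are not efficacy tables. No planned efficacy table separates the two schedules.
- *Disease category.* Part 1 Expansion Arms 1 and 2 are set by age and transplant history, with no limit on time to relapse. A first relapse more than 1 year after initial treatment, without allogeneic transplant and not refractory, fits none of the four Phase 2 categories but can enter the pool.
- *The SAP's own subtypes.* Subgroup 15, planned for the combined group only, adds a fifth subtype, "subjects who have failed 2 or more cycles of first line therapy". As worded it is not one of the four, which indicates that the pool is not restricted to Phase 2-eligible subjects. Subgroup 15 has no row for the late first relapse.

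**4. Size, as illustration only.** The documents give no count of non-qualifying subjects. Shift in ORR = non-qualifying share × ORR difference.

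Assumptions: five subjects each on 100 mg QD and 50 mg BID in dose escalation, all R/R AML; 0 to 40% of the Phase 1 QD subjects not Phase 2-eligible; an ORR difference of 10 to 20 points. Scenario A takes Arms 1 and 2 at their minimum of 25 each; scenario B doubles them.

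| | A | B |
|---|---|---|
| Pool | 125 + 50 + 5 + 5 = 185 | 125 + 100 + 5 + 5 = 235 |
| 50 mg BID only | 5/185 = 2.7%; shift 0.3 to 0.5 | 5/235 = 2.1%; shift 0.2 to 0.4 |
| With 40% of QD ineligible | 5 + 0.4 × 55 = 27; 14.6%; shift 1.5 to 2.9 | 5 + 0.4 × 105 = 47; 20.0%; shift 2.0 to 4.0 |

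These are not bounds: the arm sizes are minimums and extra escalation subjects are allowed.

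**5. Precision cost of restricting.** Exact 95% CI widths at an ORR near 36%, scenario A: 67/185, 14.3 points; 65/180 (BID removed), 14.5; 57/158 (all 27 removed), 15.5. Scenario B: 85/235, 12.6 points; 68/188 (all 47 removed), 14.2.

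**The case against.** The strongest case against is that nothing is decided on this pool. The success criterion belongs to Phase 2, SAP 10.1 says the efficacy analyses aim at estimation, and Phase 1 and Phase 2 are also reported separately. This stands, and it limits the severity. The word primarily in SAP 10 selects the 100 mg group within the combined tables; it does not rank the pool above Phase 2.

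The protocol's wording is permissive. That makes pooling optional, but it does not remove the conditions attached to it. Protocol 12.6 requires deviations to appear in the study report, which is a second disclosure route but does not replace Section 13. Exclusion 6 (potentially curative therapy available) applies to all parts and may remove some late first relapses, though it does not reproduce the four categories. Subgroups 6, 9 and 14 describe the mix further, and none isolates the late first relapse.

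Three stronger readings are tempting and the documents do not support them.
- *That the wider pool could rescue a missed Phase 2 criterion.* For example, 41/125 (lower bound 24.7%) plus 16/44 gives 57/169, lower bound 26.7%. But the 25% threshold does not apply to the pool, the 44 subjects at 100 mg QD are not stated to be R/R AML, and the movement comes from pooling itself, which the protocol permits.
- *That Phase 1 subjects lack central IDH2 confirmation.* Central testing of Phase 1 samples is planned retrospectively. The difference is mainly timing, with no stated rule for discordant results.
- *That the combined ORR is biased by a known amount.* The ineligible share and the ORR difference are assumptions. No passage reports a response difference between schedules.

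**Conclusion.** The inconsistency is real and rests on the text alone. The SAP's main combined group omits two explicit protocol conditions, replaces the supportive label with a claim of robustness, and leaves the change out of Section 13. The pivotal Phase 2 analysis is intact. The effect on the combined ORR, CRR, DOR and OS cannot be determined from the documents. Under the stated assumptions the schedule issue alone moves ORR by 0.2 to 0.5 points, and both issues together by up to 2.9 points (scenario A) or 4.0 points (scenario B). Severity is minor to moderate: it merits correction because the repair is cheap, and because the combined estimates otherwise describe a population that the protocol did not define.

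**What to change.** - Add the protocol-defined pool for the combined ORR, CRR, DOR and OS, and report it beside the total-daily-dose pool: Phase 2 subjects plus Phase 1 R/R AML subjects assigned 100 mg QD who fall in one of the four Phase 2 categories, with a positive central IDH2 result and no prior IDH inhibitor, as far as recorded.
- Treat the fifth subtype in SAP 8.2.1 item 4 as outside the four categories unless the subject also meets one of them.
- Add a row to subgroup 15 for other subjects, not in a Phase 2 category.
- In SAP 10.2, call the combined analyses supportive in place of the robust-estimate wording.
- In Section 13, list the total-daily-dose pool as a departure from Protocol 12.5.1 and 12.5.7.

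The cost is one regimen filter, one derived flag and one more set of tables, with the slightly wider intervals shown above in the restricted pool. R/R subtype and local and central IDH2 results are already planned baseline variables (SAP 8.2.1 items 4 and 2). The documents do not show that every Phase 2 criterion was recorded for Phase 1 subjects, and SAP Section 12 reports efficacy analyses at three earlier cut-offs, so the flag would be defined after results were seen. For both reasons the restricted pool should be added rather than put in place of the existing one.

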10.1. Multiplicity

Efficacy analyses in this single-arm study are aimed to provide treatment effect estimates. Thus, multiplicity is not of concern for this study.

10.2. Analysis of Primary Efficacy Endpoint

The primary efficacy endpoint of ORR is defined as the rate of responses including CR, CRi, CRp, PR, mCR (for MDS) and MLFS (for AML) by investigator assessment. The ORR will be summarized by the percentage of responses primarily in the FAS with 2-sided exact binomial 95% CI.

Response will also be summarized by the best objective response following the hierarchical order of CR, CRi/CRp, PR, mCR/MLFS, stable disease, relapse/progressive disease/failure, and not evaluable (NE).

An observed ORR in the pivotal Phase 2 R/R AML FAS subjects with the lower bound of the exact binomial 95% CI greater than 25% is deemed clinically meaningful and exceeds the expected ORR with other available therapies. This will be considered as evidence of clinically significant activity of AG-221. The analyses in the combined Phase 1/2 R/R AML on total daily dose of 100mg utilize larger population and thus provide robust estimate of ORR to better describe the clinical activity of AG-221.

To assess the robustness of the primary analysis, the following sensitivity analyses will be performed:

- (1) ORR in the EAS for the combined Phase 1, Phase 2, and the combined Phase 1/2;

- (2) The ORR assessed by Independent Response Adjudication Committee (IRAC) in the FAS for Phase 1, Phase 2, and the combined Phase 1/2 R/R AML.

10.3. Analyses of Secondary Efficacy Endpoints

The key secondary endpoints include the rates of CR, CR/CR_h and CR/CR_i/ CR_p, DOR, OS, and 56-day independence of RBC and Platelet transfusion. In addition, the following secondary efficacy endpoints are being evaluated as well: EFS, DOCR, DOCR/CR_h, TTR, TTBR, TTCR, and TTCR/CR_h.

Kaplan-Meier (KM) methods will be utilized to estimate time-to-event endpoints. Counts and percentages will be used to describe categorical variables. Mean (SD), median, and range will be provided to descriptively summarize continuous variables.

10.3.1. Key Secondary Efficacy Endpoints

10.3.1.1. Complete Response Rate

CRR is defined as the rate of CR according to modified IWG response criteria.

Number and percentage of subjects with CR and the 2-sided exact binomial 95% CI for CRR will be summarized for Phase 1 dose escalation, Part 1 Expansion, the combined Phase 1, Phase 2, and the combined Phase 1/2 for the FAS as described in items 1 to 5 of [Section 5.1](#).

The following sensitivity analyses will be performed for Phase 1, Phase 2, and the combined Phase 1/2 :

- (1) CRR in the EAS;
- (2) CRR assessed by IRAC in the FAS.

